9) Describe the research design and the procedures to be used to accomplish the specific aims of the

project. Provide a precise description of the planned data collection, analysis and interpretation. Address sample size, inclusion of women and minorities. Define in clear terms exactly what will be done to the human subjects.

Overview. The planned RCT uses a 2 (ME-CCT vs. SC) x 4 (Weeks 0, 4, 8 and 21) mixed effects experimental design. A total of 216 older participants with MCI will be recruited from the two participating sites, VASDHS and VAPORHCS (108 from each site). By including two geographically distinct sites, we will not only enhance the efficiency of our recruitment and diversity of our sample, but also demonstrate the efficacy of ME-CCT at different geographic areas with different providers. Participants will be randomized to either the ME-CCT or SC group. Participants in the CCT group will receive our ME-CCT intervention during the first 8 weeks of participation in the study, whereas SC participants will receive a robust control intervention, Goal-Focused Supportive Contact. During study participation, all participants will continue to receive their usual medical, psychiatric and psychotherapeutic care. Both groups will undergo study evaluations at baseline, 4 weeks (midway through ME-CCT), 8 weeks (immediately following ME-CCT completion) and 21 weeks (3 months after ME-CCT completion).

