Participants and eligibility criteria. Inclusion Criteria: 1) Veterans ≥ 55 years old enrolled at one of the participating VA sites (VASDHS and VAPORHCS) who are able to provide informed consent. 2) Independently living. 3) Meet criteria for MCI based on previously published criteria [9, 16]. 4) Willingness to participate in audio-recorded sessions. Exclusion Criteria: 1) Current substance use disorder with < 30 days abstinence. 2) History of schizophrenia, schizoaffective disorder, or other primary psychotic disorder. 3) History of significant brain injury with loss of consciousness > 30 minutes. 4) Auditory or visual impairments that would prevent ability to participate in the cognitive rehabilitation group or benefit from compensatory strategies. MCI Criteria: Criteria for MCI will be based on previously published criteria [9, 16]: 1) Concern about a decline in cognitive functioning expressed by a physician, informant, participant or nurse. 2) Cognitive impairment in one or more of the following domains: executive function, memory, attention, language or visuospatial abilities. 3) Normal or minimal impairment in functional activities. 4) Does not meet criteria for dementia. To determine whether individuals meet criteria for MCI, two neuropsychologists (Drs. [name], [name], [name], or [name]) will separately review each individual's neuropsychological performance on a comprehensive neuropsychological battery (see **Table 6**) to determine study eligibility and classify MCI subtypes. If there are discrepancies, a third neuropsychologist will review the data and the participant will only be included if consensus can be reached. The standard clinical neuropsychological assessment batteries conducted with adults with MCI through the Neuropsychology Clinics at the VASDHS and VAPORHCS sites are typically much longer (often exceeding three hours), and adults with MCI tolerate these batteries well. All subtypes of MCI will be included; however, in order to facilitate exploratory analyses to determine whether ME-CCT is more effective for particular subtypes, participants will be classified as follows, using previously published criteria [9, 16] and procedures similar to those we have used in our previous studies [73]: A) Single domain amnestic MCI will be operationally defined as performance on at least two memory measures falling ≥ 1 standard deviation (SD) below their age-appropriate norms. B) Single domain non-amnestic MCI will be operationally defined as performance on at least two measures in one domain of the above mentioned cognitive domains falling ≥ 1 SD below their age-appropriate norms in the absence of memory impairment. C) Multiple domain amnestic MCI will be defined as meeting the above criteria for a memory deficit as well as meeting criteria for a deficit ≥ 1 SD below their age-appropriate norms on at least two measures within one or more of the additional cognitive domains (attention/processing speed, language, executive functioning). D) Multiple domain non-amnestic MCI will be operationally defined as performance on at least two measures in more than one of the above mentioned non-memory cognitive domains falling ≥ 1 SD or more below their age-appropriate norms in the absence of memory impairment.

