
Recruitment and feasibility. Total enrollment for the study will be 108 participants per site (54 ME-CCT and 54 SC per site), for a total of 216 participants (108 ME-CCT and 108 SC). Participants will be primarily recruited through clinic referrals and medical record review followed by recruitment letters sent to patients who meet the requisite pre-screening criteria. The recruitment letter will state that the individual may opt out by calling the research team indicating that they do not wish to be contacted, or they may indicate they are interested in learning more about the study by calling the study team. The letter will state that if the individual has not responded to the letter within two weeks, research personnel will contact them by phone. Participants will also be recruited through other research study referrals and contacted by letter /phone (see Section 11: Recruitment for more recruitment methods). We will recruit a sample composed of at least 25% of individuals from ethnic/racial minority groups, including African Americans, consistent with the 2013 US Census. This will provide us with enough subjects to explore minority status as a moderator of treatment outcome, although we do not expect differential effects. By having two sites, we will be better able to ensure adequate ethnic/racial diversity in our sample. We will recruit women and men. At the VASDHS, over the past year approximately one third of the 500+ total referrals to the Neuropsychological Assessment Unit were diagnosed with MCI and likely would have been eligible for the proposed study. At VAPORHCS, 2,472 Veterans with a diagnosis of MCI were treated over the past two years; moreover, within the past year, of the 336 neuropsychological assessments conducted through the VAPORHCS Neuropsychology Clinic, 129 of those (59%) resulted in a diagnosis of MCI and likely would have been eligible to participate in the proposed study. At the VAPORHCS, since January 2015, 125 patients have been referred for the waiting list for the ME-CCT intervention; all referrals came from clinicians who had heard about the groups through word of mouth. We did not implement any intensive research recruitment efforts such as those proposed in this study (e.g., advertisements, letters to eligible patients, study compensation, study coordinators with protected time to seek out referrals). This demonstrates not only recruitment feasibility but also genuine interest in the groups, both by patients and the clinicians who refer them. Based on these data, we estimate that over 250 adults per year will be eligible to participate in the proposed study between the two sites, indicating that the goal of recruiting 216 participants over the course of the five-year study is very feasible. Nevertheless, should our VA recruitment efforts prove less successful than we anticipate,

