
we will recruit additional participants from the academic institutions affiliated with each participating VA, namely University of California, San Diego (UCSD) and Oregon Health & Science University (OHSU), where Drs. [name] and [name] have joint appointments, respectively. UCSD programs that can refer participants include Senior Behavioral Health and the Memory and Resilience Center (see letter of support from [name], Medical Director and Co-Director of these two outpatient programs). At UCSD, the Senior Behavioral Health Program and the Memory, Aging, and Resilience Center evaluate and treat about 75 patients per year with MCI. OHSU programs that can refer participants include the National Institute on Aging (NIA)-funded Layton Aging & Alzheimer's Disease Center (Directed by Co-Investigator [name]) and the OHSU Division of General Internal Medicine and Geriatrics (Directed by Co-Investigator [name]) (see letters of support from Drs. [name] and [name]). At OHSU, the Layton Center longitudinally follows about 450 research volunteers at risk for MCI or dementia, and enrolls 60 new volunteers per year.

Retention and reimbursement. We had a relatively low non-completer rate (11%) among subjects enrolled in our funded CCT study with OEF/OIF Veterans with mild TBI; moreover, all of the non-completers dropped out prior to the start of the group, while those who attended the first session of the group completed the 10-week CCT intervention. The five ME-CCT for MCI groups that we have run at VAPORHCS have had a similar drop-out rate of ~10%. We have, therefore, conservatively assumed a 20% drop-out rate and will recruit 216 participants to yield a final sample size of 180. Our power analyses were calculated assuming 20% attrition, yielding a total final sample of n=180 (see power analyses for each hypothesis). We will use subject compensation and reminder phone calls to reduce our attrition rate. Participants will be compensated \$50 after each of the first three assessments, and \$75 after the fourth and final follow-up assessment. If participants complete all four assessments, their total compensation will be \$225. VASDHS participants who elect to use the Fitbit during the study will be able to keep the Fitbit device at the conclusion of their study participation.

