Section 9.11 Pictures and Audio/Video Recordings of Patients

9.11) Describe the purpose and of photographs (facial) or audio or video recordings of patients

Audio recordings are necessary for the purpose of assessing therapist fidelity to the intervention.

Section 10 - Human Subjects

10) Describe the characteristics of the proposed subject population. Include age, gender, ethnicity, and health status as appropriate. Provide inclusion and exclusion criteria as appropriate. Indicate the number of VASDHS participants to be studied. For multisite studies, also provide the total number of subjects from all sites. Indicate the estimated number of consented subjects that will fail the screening process, if any.

Inclusion Criteria: 1) Veterans >55 years old enrolled at one of the participating VA sites (VASDHS and VAPORHCS) who are able to provide informed consent. 2) Independently living. 3) Meet criteria for MCI based on previously published criteria [9, 16]. 4) Willingness to participate in audio-recorded sessions.

Exclusion Criteria: 1) Current substance use disorder with < 30 days abstinence. 2) History of schizophrenia, schizoaffective disorder, or other primary psychotic disorder. 3) History of significant brain injury with loss of consciousness > 30 minutes. 4) Auditory or visual impairments that would prevent ability to participate in the cognitive rehabilitation group or benefit from compensatory strategies. MCI Criteria: Criteria for MCI will be based on previously published criteria [9, 16]: 1) Concern about a decline in cognitive functioning expressed by a physician, informant, participant or nurse. 2) Cognitive

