For eligible individuals identified by study staff through clinic referrals/medical record review, the study staff will send a recruitment letter (or contact by phone if the Veteran gave their verbal permission to being contacted by phone). The letter will state that the individual may opt out by calling the research team indicating that they do not wish to be contacted, or they may indicate they are interested in learning more about the study by calling the study team. The letter will state that if the individual has not responded to the letter within two weeks, research personnel will contact them by phone. Study Personnel will respond to calls from individuals who are interested in the study to answer any questions they might have about the study and to schedule an Initial Study Visit if they remain interested. If no response to the letter is received within two weeks, the research team will contact the individual by phone but with limited interaction. During this follow-up phone call, the researcher will identify themselves, explain why they are calling, and ask if the individual received the letter. If they did, the researcher will ask if they have reviewed the letter and whether or not they are interested in hearing more about the study. If the individual has received, but not reviewed, the letter, the researcher may ask if they are interested in hearing more about the study or receiving more information. After answering their questions, the researcher will schedule an Initial Study Visit for those who state they are interested in participating. If the Veteran has not received the letter, the researcher will only ask permission to send a second letter and confirm the individual's address; no other information will be requested at that time.

Individuals referred from other VA IRB-approved research studies (who gave their consent to be contacted about additional research opportunities), will also be sent a recruitment letter via mail prior to being contacted by phone, unless they have specifically consented to phone contact. If no response to the letter is received within two weeks, research personnel will follow the same follow-up phone call procedures as stated in the previous paragraph. Studies we will recruit from include protocol numbers: H170028, H160090, H140057, H130022, and H160022, and other applicable VA studies with older Veterans with MCI.

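### Veterans who have already had ME-CCT, CCT or CogSMART are not excluded, although one of the two sites has run five ME-CCT groups; any who enrol would probably attenuate the treatment contrast, by an unknown and probably modest amount.

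*Combined protocol and SAP*

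**What the plan says.** **Eligibility.** In Section 9 (Participants and eligibility criteria) the list opens "Exclusion Criteria: 1) Current substance use disorder with < 30 days abstinence. 2) History of schizophrenia, schizoaffective disorder, or other primary psychotic disorder". Its third item covers head injury with prolonged unconsciousness, and the fourth and last reads "4) Auditory or visual impairments that would prevent ability to participate in the cognitive rehabilitation group or benefit from compensatory strategies". Section 10 repeats this list, and the lay summary in Section 5 gives the same four items in slightly different words. The inclusion criteria cover age and site enrolment, independent living, MCI, and willingness to be recorded. Pre-screening and recruitment (Sections 9 and 11) provide for a chart review and an eligibility phone call, but neither is said to ask about earlier cognitive training. Prior training is not a named covariate or moderator in the analysis plan.

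**Earlier delivery of the intervention.** Section 9 (Retention and reimbursement) reports: "The five ME-CCT for MCI groups that we have run at VAPORHCS have had a similar drop-out rate of ~10" per cent. Section 9 (Recruitment and feasibility) adds that at the same site, since January 2015, "125 patients have been referred for the waiting list for the ME-CCT intervention". Section 9 (Secondary Outcomes) refers to a CogSMART pilot in adults with MCI. The trial recruits through clinic referrals, record review and other studies: five numbered protocols "and other applicable VA studies with older Veterans with MCI" (Section 11).

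**Contamination safeguards.** Section 9 keeps the groups apart, asks Veterans not to discuss their treatment, and rates a sample of SC sessions with the ME-CCT fidelity tool. Any score above zero triggers a review.

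**The concern.** A Veteran who attended one of the Portland ME-CCT groups and still has MCI meets every criterion as written. The safeguards act on what happens during the trial and do not address skills a participant brings to it.

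Two routes could reduce the contrast:

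- **Smaller gain in ME-CCT.** H1 is tested as treatment by time, and the power calculation takes the slope as the outcome. Someone who repeats the course probably has less left to gain. The protocol itself reports that strategy use on the PCSS rose after ME-CCT in its pilot, so former trainees may also start higher on that exploratory mediator.
- **Sharing in SC.** SC members are encouraged to seek advice from each other. A former trainee in an SC group, which may have as few as six members, could pass on ME-CCT strategies. The fidelity tool might detect this in a rated session but could not undo it.

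Randomisation spreads former trainees over both arms in expectation, so the main consequence is attenuation and lost power. Chance imbalance is possible, because whole groups are randomised and the known ME-CCT exposure is at one site.

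**Working it through.** **Inputs from Section 9 (H1 power analysis; Recruitment and feasibility).** Two-sided alpha .02; 0.5 SD at the last time point; 180 completers, so 90 per arm at 1:1 allocation; stated power at least 85%.

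**Reproducing the plan's figure.** Using a simple two-group comparison at the last time point:

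- Noncentrality = 0.5 × √(90/2) = 3.354.
- Critical value = 2.326.
- Power = Φ(3.354 − 2.326) = Φ(1.028) = 84.8%, which matches 85%.

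The match is to this simple comparison. A linear-slope calculation with the plan's autoregressive correlation of .45 gave 57% to 65%, depending on visit spacing. Also, 216 less 20% is 172.8, not 180; at 86.4 per arm the simple power is 83.1%. Both are separate matters. Here the stated 85% and 180 are taken at face value, so the figures below show the loss relative to the plan.

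**Attenuation.** Let f be the pre-trained share in both arms and r the fraction of the ME-CCT versus SC effect that remains in pre-trained people. Then

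difference = 0.5 × [1 − f(1 − r)].

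The documents give neither f nor r; both are assumptions.

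| f (of 216) | r = 0: difference, power | r = 0.5: difference, power |
|---|---|---|
| 0 | 0.500, 84.8% | 0.500, 84.8% |
| 2.5% (about 5) | 0.488, 82.7% | 0.494, 83.8% |
| 5% (about 11) | 0.475, 80.5% | 0.488, 82.7% |
| 10% (about 22) | 0.450, 75.6% | 0.475, 80.5% |

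Example, f = 5% and r = 0: 0.475 × √45 = 3.186; Φ(3.186 − 2.326) = Φ(0.860) = 80.5%.

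The plan's own floor is 80% for every hypothesis. With r = 0, H1 falls below it at f of about 5.6%, or 12 of 216. With r = 0.5 the share doubles to about 11.2%, or 24 of 216. H3 is planned at exactly 80%, so any attenuation takes it under.

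**How large could f be?** The sizes of the five earlier groups are not given. At an assumed 6 to 8 per group (6 is this trial's minimum), 5 × 6 = 30 to 5 × 8 = 40 Veterans attended.

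- If Portland's 108 were drawn in proportion from the 2,472 Veterans with MCI treated there in two years: 108 × 40/2,472 = 1.7, so f is about 0.8% and power about 84%.
- If drawn in proportion from five years of that clinic's 129 MCI diagnoses plus the 40: 108 × 40/(645 + 40) = 6.3, so f is about 2.9%, just beyond the 2.5% row.
- The 10% row needs about 22 people, or 54% to 72% of all earlier attendees (21.6/40 to 21.6/30).

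Proportional recruitment may understate f, since people who sought this training may be readier to join. The formula also omits strategy-sharing within SC groups.

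**The case against.** The strongest reply is that no passage shows a trained Veteran being approached or enrolled. That stands, and it limits the claim to a gap of uncertain size. Several stronger readings are tempting, and the documents do not support them.

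- **That the 125 Portland referrals were exposed.** They were referred to a waiting list; how many were treated is not stated. This shows demand, not exposure.
- **That power could fall to about 64%.** That needs 20% of the sample, or 43 of 216, which is more than the 30 to 40 people the five groups would have held on the assumption above. It also needs r = 0, the worst case, in which a second 16-hour course adds nothing.
- **That pre-trained SC participants shrink the contrast directly.** They carry their skills at week 0, so their change over time need not be larger. Only the sharing route acts through SC.
- **That participants could begin a clinical ME-CCT group during the trial**, because "all participants will continue to receive their usual medical, psychiatric and psychotherapeutic care". No passage says such groups are still offered.
- **That the CCT-for-TBI cohort is a substantial source.** Those were OEF/OIF Veterans of unstated age, and no overlap with Veterans of 55 or more with MCI is shown.
- **That a null result could not be separated from earlier exposure.** The plan tests site and its interaction with treatment, collects the PCSS at week 0, adjusts for baseline differences, and examines baseline outcome performance as a moderator. These are partial safeguards; none identifies who was trained.

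One could also hold that recording exposure and adding a sensitivity analysis would suffice, without narrowing the population. That is a fair alternative, and the only one for participants already enrolled. For future enrolment, exclusion fits better with a protocol that tolerates no ME-CCT content in SC.

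**Conclusion.** The omission is certain: no eligibility list and no screening step addresses prior ME-CCT, CCT or CogSMART, although one recruiting site has delivered ME-CCT to the target population. The consequence is possible attenuation of the ME-CCT versus SC difference, of unknown and probably modest size. On the plan's own 85% for H1, 2.5% to 5% pre-trained would cost about 2 to 4 percentage points at worst and 1 to 2 if half the effect remains. At 10% the loss would be about 9 or 4 points respectively. These figures rest on assumed values of f and r, on assumed sizes of the earlier groups, and on the stated power. This is an inexpensive improvement worth making. It does not show that the trial's result would be biased or uninterpretable.

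**What to change.** Add one exclusion to the lists in Sections 5, 9 and 10: prior or current participation in ME-CCT, CCT or CogSMART, whether clinical or research. Check it at the existing chart review and eligibility call, against each site's own group rosters. A broader bar on any structured cognitive training is not needed on the evidence in the documents.

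For anyone already enrolled, record prior exposure from charts and rosters, without knowledge of allocation, and report the count by arm and site. Pre-specify a sensitivity analysis of H1 that omits these participants. Because exposure predates randomisation, omitting them does not select on anything the treatment could have changed.

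The cost is one eligibility amendment and a roster check. At 6 to 8 per earlier group, at most a few dozen otherwise eligible Veterans would be lost from a pool the protocol puts at over 250 per year across the two sites.

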Dependent variables: Neurocognitive composite score (Average z score across subtests in the Neurocognitive Battery detailed in **Table 6**); Functional capacity composite score (Average z score across subtests in the Functional Capacity Battery detailed in **Table 7**). **Independent variables:** Treatment group (2 levels, ME-CCT and SC), and Time (4 levels, Weeks 0, 4, 8, 21). **Statistical Analysis:** We will analyze data on all randomized subjects for whom we have a baseline assessment and at least one post-baseline evaluation. Data will be analyzed by mixed effects model methods [91-93] for linear or non-linear trends based on earlier inspection of data. The mixed effects model method provides an estimate of the individual variability around the population trend, the variability of the individual intercepts (baseline values) and slopes (changes across time), and the correlation between them. A fully saturated treatment X time model will be utilized for inference. Covariance structure will be chosen based on Akaike's Information Criterion (AIC). Random group level treatment effects will also be evaluated for importance based on the model AIC. Denominator degrees of freedom will be calculated using the Kenward-Roger small sample correction. The effects of site, therapist and their interaction with treatment will be included and tested. However, we do not anticipate any significant interactions or main effects of these factors given our balanced study design (equal numbers at each site in each group), our standard training and operating procedures at both sites and with all therapists, and our previous analyses from our similarly-designed study (our CCT for TBI study). In any case, the analysis procedures will include these factors and their interaction effects to avoid allowing site or therapist effects to bias treatment comparisons. If we detect any imbalances between the treatment groups, we will follow the primary analyses above with subsequent analyses considering the imbalances to verify that the conclusions are not affected by the imbalances. Analyses will be conducted within and across nested levels of the study design; this will involve within-subject analyses (comparison of occasions of measurement nested within an individual), as well as between-subject analyses. In addition, any treatment group comparison will be adjusted for subject-specific characteristics, and adjustments for changes in these characteristics over the course of the study can be incorporated into the single-subject analyses. **Power Analysis:** In addition to the procedures described by Hedeker and colleagues [94] for Random Regression Models (the RMASS program provided by Hedeker), we used several standard other methods for power calculation and estimation of needed sample size. We selected the sample size that would provide us with a minimum of 80% power across all hypotheses and their expected effect sizes. We used this method with the following assumptions to estimate required sample size: the mixed design of two groups (ME-CCT and SC) and time (4 levels, weeks 0, 4, 8, 21) where the slope is the dependent measure; alpha-level of .02, nature of the hypothesis (two-sided), dropout rate (up to 20%), autoregressive covariance structure (with correlation between sequential assessments set at .45) of the longitudinal data, medium effect size as a between-group difference increasing linearly from 0 at baseline to .5 SD units at the last time point, various correlations (.2, .5, and .8) between the repeated measures, and various effect sizes from medium to large. We estimated that with a final sample size of 180 participants (216, with a drop-out rate of 20%), the study will have

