
minimum 85% power to yield a statistically significant result for a medium effect size. As is noted in the previous sections, we have found medium to large post-treatment effect sizes for several outcome measures in our previous studies.

H2: Compared to those in SC, participants in ME-CCT will show significant improvements on measures of subjective cognitive complaints, subjective functioning, and collateral measures of everyday functioning.

Dependent variables: Subjective Everyday Functioning Composite Score (average total score across the two Neuro-QOL scales, namely the Applied Cognition Executive Function Scale, and the Applied Cognition General Concern Scale); ECog.

Independent variables: Treatment group (2 levels, ME-CCT and SC), and Time (4 levels, Weeks 0, 4, 8, 21). Statistical Analyses: Data will be analyzed similar to the method described for H1. Power Analyses: Power analyses were conducted similarly to H1, and the study will have 87% power to yield a statistically significant result for a medium effect size for H2. We have found large effects on subjective cognitive/functional complaints in previous studies.

H3: Compared to those in SC, participants in ME-CCT will show increased participation in protective activities, as measured by physical and cognitive activity inventories.

Dependent variables: Cognitive Activity Inventory, CHAMPS Physical Activity Inventory for Older Adults. Independent variables: Treatment group (2 levels, ME-CCT and SC), and Time (4 levels, Weeks 0, 4, 8, 21). Statistical Analyses: Data

will be analyzed similar to the method described for H1. Power Analyses: Power analyses were conducted similarly to H1, except the alpha level was set at .01; the study will have 80% power to yield a statistically significant result for a medium effect size for each dependent measure evaluated through H3.

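### Recruiting 216 with 20% dropout leaves about 173, not the 180 on which the power for every hypothesis rests

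*Combined protocol and SAP*

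**What the plan says.** The pairing of 216, 20% and 180 appears in two places in Section 9.

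- *Retention and reimbursement*: the investigators "conservatively assumed a 20% drop-out rate and will recruit 216 participants to yield a final sample size of 180". The next sentence reads "Our power analyses were calculated assuming 20% attrition, yielding a total final sample of n=180" and refers the reader to the power analysis of each hypothesis.
- *H1, Power Analysis*: power is given "with a final sample size of 180 participants (216, with a drop-out rate of 20" per cent). The same paragraph lists dropout of up to 20% among the inputs and says the sample size was chosen to give "a minimum of 80% power across all hypotheses and their expected effect sizes".

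The stated powers for a medium effect are at least 85% for H1 (two-sided alpha .02); for H2, "the study will have 87% power to yield a statistically significant result for a medium effect size for H2"; and for H3, as H1 "except the alpha level was set at .01; the study will have 80% power to yield a statistically significant result". The H2 and H3 calculations are described as similar to H1.

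The H1 analysis covers "all randomized subjects for whom we have a baseline assessment and at least one post-baseline evaluation". On earlier experience, *Retention and reimbursement* gives 11% non-completion in the mild TBI trial, where "all of the non-completers dropped out prior to the start of the group", and about 10% in five ME-CCT groups for MCI.

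**The concern.** A 20% loss from 216 cannot leave 180. The sample that the plan's own conservative assumption delivers is therefore smaller than the one to which all three power statements are tied. H3 is stated at exactly the 80% minimum, so it has no room for any reduction.

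A related gap concerns H2. The ECog is one of its two dependent variables, but under *Assessment Methodology* collateral informants contribute only when available. Having an informant is not an eligibility criterion in Section 9 or Section 10, and no availability rate is given. One power figure of 87% is stated for H2 with no allowance for this.

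**Working it through.** **Sample size.** Inputs from *Retention and reimbursement*: 216 recruited, 20% dropout, 180 remaining.

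- Remaining after 20% loss: 216 × (1 − 0.20) = 172.8, or 86.4 per arm.
- Loss implied by 216 to 180: 1 − 180/216 = 16.7%.
- Recruitment needed for 180 after 20% loss: 180 / 0.80 = 225.
- The plan's pair is reproduced exactly by 180 × 1.20 = 216. That is consistent with adding 20% of the final N instead of dividing by 0.80, though the working is not shown.

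**Checking the stated powers at 180.** For a simple two-group comparison of means with a 0.5 SD difference, power = Φ(0.5 × √(n/2) − z), with n per arm and z the two-sided critical value.

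- H1, alpha .02 (z = 2.326), n = 90: Φ(3.354 − 2.326) = 84.8%, which agrees with the stated 85%. At n = 86.4: Φ(3.286 − 2.326) = 83.1%.
- H3, alpha .01 (z = 2.576), n = 90: 78.2%, somewhat below the stated 80%. At n = 86.4: 76.1%.

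The sponsor's actual method cannot be confirmed. A slope model with the stated autoregressive correlation of .45 gave about 57–65% for H1 at 180, whereas compound symmetry at .45 with four visits gave 85.2–85.8%. The next step therefore takes the stated powers as given and asks only what the smaller N does to them.

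**Scaling the stated powers.** Let δ = z + Φ⁻¹(stated power). Then power at N = Φ(δ × √(N/180) − z). For N = 172.8, √(172.8/180) = 0.980.

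| Hypothesis | alpha | δ | Stated at 180 | At 172.8 |
|---|---|---|---|---|
| H1 | .02 | 2.326 + 1.036 = 3.363 | 85% (a minimum) | 83.4% |
| H2 | .02 (inferred) | 2.326 + 1.126 = 3.453 | 87% | 85.5% |
| H3 | .01 | 2.576 + 0.842 = 3.417 | 80% | 78.0% |

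The alpha for H2 is inferred from the statement that it was done like H1; any alpha from .01 to .05 gives 85.4–85.6%. If the 80% for H3 was rounded from somewhere between 79.5% and 80.5%, the result is 77.5–78.5%. H3 would need 81.9% at 180 to hold 80% at 172.8.

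**ECog, illustration only.** No availability rate is given, so the rates below are assumptions. They are applied to 172.8 and use the H2 scaling (alpha .02).

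| Assumed share with an informant | N | ECog power |
|---|---|---|
| 90% | 155.5 | 81% |
| 80% | 138.2 | 76% |
| 70% | 121.0 | 69% |
| 60% | 103.7 | 62% |

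Power of 80% is reached at N = 180 × ((2.326 + 0.842)/3.453)² = 151.5, about 152 participants with an informant, or 88% of 173. For alpha between .05 and .01 the threshold is about 148 to 153.

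**The case against.** The strongest reply is that 20% is deliberately pessimistic. Earlier loss was 10–11%, which would leave 216 × 0.89 = 192 to 216 × 0.90 = 194. The same scaling then gives about 87.5% for H1, 89% for H2 and 83% for H3, all above the stated values. This stands as a reason not to worry about the trial's actual power. It does not repair the calculation, because 20% is the case the sponsor chose to plan for.

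Second, the inputs to the H1 power calculation speak of dropout up to 20%, which a 16.7% loss satisfies. That supports reading the slip as loose wording. But *Retention and reimbursement* says 20% was assumed and yields 180, and the H1 paragraph itself sets 180 beside a 20% rate.

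Third, the mixed model keeps leavers who have any post-baseline evaluation, so the analysed sample may exceed 173. That is correct, and 173 is the low end. It applies if leavers go before any post-baseline visit, which is the pattern suggested by the earlier trial, where non-completers left before the group began. The plan does not say whether those people had been randomised; anyone who leaves before randomisation would not count as a loss from the analysis set.

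Fourth, dropout is listed as an input to the power calculation, and how it entered is not shown. Scaling from 180 may therefore not match the sponsor's own correction. This limits the precision of the power figures but not the 172.8.

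Fifth, the ECog point is a separate matter and its availability rates are assumed. That is so, and the main finding does not depend on it.

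**Conclusion.** The concern holds. The figure of 180 is wrong as written in both places: 216 less 20% is 172.8, a shortfall of 7.2 participants. The cost in power is about 1.5 to 2 percentage points. H1 and H2 stay above the plan's 80% minimum; H3 falls just under it, to about 78%. The arithmetic on N is exact. The powers are approximate and rest on three assumptions: that the stated powers were obtained at 180, that power scales with √N, and that all leavers are lost to the analysis. This should be corrected, but it does not threaten the primary comparison.

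**What to change.** In *Retention and reimbursement* and in the H1 power paragraph, use one consistent set of figures:

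- **Either** 216 enrolled, 20% dropout, final N of about 173, with the H1, H2 and H3 powers recomputed by the sponsor's own method. If H3 then comes out below 80%, say so beside the statement of the 80% minimum.
- **Or** 216 enrolled, 16.7% dropout, final N of 180, with the stated powers kept, provided the sponsor confirms they were calculated at 180 with no further attrition.

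In the H2 paragraph, state the expected share of participants with an informant and give ECog power separately at that number.

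The cost is text and one recalculation. Under the first option the stated powers become about 1.5 to 2 points less favourable. No extra enrolment is required; holding both 20% dropout and 180 remaining would instead mean recruiting 225.
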